1. PROJECT TITLE

A Randomized, Subject-Masked, Active-Controlled, Parallel-Arm Clinical Trial Comparing Erector Spinae and Paravertebral Nerve Blocks

3. FACILITIES

UCSD hospitals and the UCSD CTRI

4. ESTIMATED DURATION OF THE STUDY

Three years (1 month preparation, 24 months enrollment, 11 months publication prior to closure)

5. LAY LANGUAGE SUMMARY OR SYNOPSIS (no more than one paragraph)

Following painful surgical procedures of the breast, postoperative analgesia is often provided with a paravertebral nerve block (PVB). For intense, but shorter-duration acute pain, a single-injection of local anesthetic is used with a duration of approximately 12 hours. Recently an alternative block has been reported: the erector spinae plane block.² The theoretical benefits include ease of administration since it is a plane superficial to the PVB and therefore easier to identify and target with ultrasound (therefore increasing success rate); and an increased safety margin as there are fewer anatomic structures in the immediate area which could be injured with the needle; and, the target plane is much further from the intrathecal/epidural space relative to the PVB, therefore leakage of cerebrospinal fluid or injury to the spinal cord are less likely with the erector spinae over the PVB. Unfortunately, it remains unknown if the analgesia provided by this new technique is comparable to that provided with the PVB.⁴ We therefore propose to compare these two techniques with a randomized, subject-masked, active-controlled, parallel-arm clinical trial.

6. SPECIFIC AIMS

The overall objective of the proposed research is to determine the relative risks and benefits of erector spinae plane versus paravertebral blocks for single-injection local anesthetic administration.

Hypothesis 1: Following breast surgery, **analgesia** will be non-inferior in the recovery room with an erector spinae plane block compared with a paravertebral block as measured with the Numeric Rating Scale.

Hypothesis 2: For breast surgery, **opioid** consumption will be non-inferior in the operating and recovery rooms with an erector spinae plane block compared with a paravertebral block (primary: cumulative intravenous morphine equivalents).

Primary end point: In order to claim that erector spinae plane blocks are non-inferior to paravertebral blocks, both Hypotheses 1 and 2 must be at least non-inferior.

7. BACKGROUND AND SIGNIFICANCE

Following painful surgical procedures of the breast, postoperative analgesia is often provided with a

paravertebral nerve block (PVB). For intense, but shorter-duration acute pain, a single-injection of local anesthetic is used with a duration of approximately 12 hours. The PVB has several limitations: it can decrease blood pressure, and very rare—but serious—complications have occurred, including neuraxial injection, neuraxial hematoma, and pleural puncture.¹ An alternative block has been described: the erector spinae plane block.² The theoretical benefits include ease of administration since it is a plane superficial to the PVB and therefore easier to identify and target with ultrasound (therefore increasing success rate); and an increased safety margin: there are few anatomic structures in the immediate area which could be injured with the needle; and, the target plane is much further from the intrathecal/epidural space relative to the PVB. Lastly, the plane may be easier to catheterize for continuous peripheral nerve blocks relative to the relatively-small volume PVB.³

There are therefore multiple *theoretical* reasons to prefer the erector spinae plane block. Unfortunately, it remains unknown if the analgesia provided by this new technique is comparable to that provided with the PVB.⁴ We therefore propose to compare these two techniques with a randomized, subject-masked, active-controlled, parallel-arm, human subjects clinical trial.

8. PROGRESS REPORT

There are no preliminary or pilot study data.

9. RESEARCH DESIGN AND METHODS

This investigation will be a randomized, subject-masked, active-controlled parallel-arm, human subjects clinical trial. Of note, we will be using standard-of-care local anesthetic under an FDA-approved purpose and do not plan to research a possible change of indication or use of these medications as part of this research project. The treatments in both groups are currently used at our institution and there is true clinical equipoise at this time. The only difference in treatment between subjects who enroll versus those not enrolled in this study will be those who enroll will have the decision between which anatomic block location determined randomly, as opposed to the physician simply choosing him/herself.

Enrollment. Consenting adults undergoing breast surgery with a planned single-injection regional analgesic will be offered enrollment. Patients undergoing breast surgery with a planned perineural catheter regional analgesic will be excluded. Study inclusion will be proposed to eligible patients prior to surgery. If a patient desires study participation, written, informed consent will be obtained using a current UCSD IRB-approved ICF. Selection for inclusion will not be based on gender, race, or socioeconomic status. The study population of interest includes men and women of all races and socioeconomic status. Inclusion and exclusion criteria are listed in section #9 below.

Preoperative Procedures. Following written, informed consent, we will collect baseline anthropomorphic information (e.g., age, sex, height, and weight). All subjects will have a peripheral intravenous (IV) catheter inserted, standard noninvasive monitors applied, supplemental oxygen administered via a nasal cannula or face mask, and placed in the sitting position. Midazolam and fentanyl (IV) will be titrated for patient comfort, while ensuring that patients remain responsive to verbal cues. Both possible block locations will be viewed with ultrasound. If one or both of the locations is unacceptable for block placement in the clinician's opinion, the subject will not be randomized and will not proceed further with the study.

Subjects will then be randomized using a computer-generated list and opaque, sealed envelopes to

one of two treatment groups: (blocks of 4, stratified for unilateral vs. bilateral surgery): (1) erector spinae plane or (2) paravertebral block. All blocks will be placed by a regional anesthesia fellow or resident under the direct supervision and guidance of a regional anesthesia attending (or by the attending him/herself).

The area of needle insertion will be cleaned with chlorhexidine gluconate and isopropyl alcohol. All blocks will be placed using standard UCSD ultrasound-guided techniques as previously described.^{4,5}

Ropivacaine 0.5% (with epinephrine 1:200,000-400,000) will be administered via the needle into the target plane. For erector spinae plane blocks, this will be at the T3 level for surgery involving the axilla and the T4 level for surgery not involving the axilla (20 mL of local anesthetic for unilateral surgery; 16 mL of local anesthetic each side for bilateral surgery). For PVBs without axillary work, this will be at the T3 and T5 levels. For PVBs with axillary work, this will be at the T2 and T4 levels. For unilateral PVBs, 10 mL of local anesthetic will be injected per level. For bilateral PVBs, 8 mL of local anesthetic will be injected per level.

Single-injection blocks will be considered successful if, within 30 minutes, the subject experiences decreased sensation to cold temperature with an alcohol pad over the approximate level of the ipsilateral 4th thoracic dermatome. Misplaced blocks will be replaced successfully, or the patient excluded from further study participation. For subjects undergoing bilateral surgical procedures, a block using the same protocol will be administered on the contralateral side.

Intraoperatively, all subjects will receive a general anesthetic using inhaled and intravenous anesthetic and oxygen. Intravenous fentanyl will be administered for cardiovascular responsiveness to noxious stimuli at the discretion of the anesthesia provider.

Postop: Subjects will be discharged with a prescription for oxycodone 5 mg tablets for supplementary analgesia and instructed to record the time at which they take their first opioid tablet as well as the time at which they believe the block starts to wear off.

Outcome measurements (end points). Pain scores will be recorded using the NRS. Within the recovery room, pain scores, opioid requirements, and antiemetic administration will be recorded by nursing staff masked to treatment group. The morning following surgery, all subjects will be contacted by phone or in person [if hospitalized] to record lowest, average, highest, and current pain scores; sleep disturbances, and nausea using a 0-10 Likert scale (0 = no nausea; 10 = vomiting). For outpatients, opioid requirements will be recorded while inpatients will have opioid requirements extracted from the electronic medical record. In addition, we will extract antiemetic use from the electronic record. We will collect the times at which subjects felt their block resolve and they consumed their first opioid analgesic pills following recovery room discharge.

Hypothesis 1: Following breast surgery, **analgesia** will be non-inferior in the recovery room with an erector spinae plane block compared with a paravertebral block as measured with the Numeric Rating Scale.

Hypothesis 2: For breast surgery, **opioid** consumption will be non-inferior in the operating and recovery rooms with an erector spinae plane block compared with a paravertebral block (primary: cumulative intravenous morphine equivalents).

Primary end point: In order to claim that erector spinae plane blocks are non-inferior to paravertebral

blocks, both Hypotheses 1 and 2 must be at least non-inferior.

Statistical methods. Descriptive statistics will be provided by arm and in aggregate. Baseline characteristics of arms will be compared using the Wilcoxon-Mann-Whitney and Fisher's Exact tests. Key characteristics that are significantly different (p<0.05) will be included as covariates in the analysis models.

Primary aim. We will test the noninferiority of the erector spinae nerve block compared to the paravertebral nerve block. The 95% confidence interval (CI) associated with the Wilcoxon-Mann-Whitney test will be derived for the group difference (paravertebral minus erector spinae) in median pain scores within the recovery room. If the lower limit of the 95% CI is greater than -1.25, we will conclude noninferiority. If there are significant differences between the groups in any key characteristics, these characteristics will be included as covariates in a linear model. The same noninferiority margin (-1.25) will be applied to the 95% CI for the covariate adjusted group difference in mean pain derived from the linear model.

The noninferiority of the erector spinae nerve block with regard to total opioid consumption within the operating and recovery rooms will be tested in the same manner as pain, i.e. comparing the limits of a 95% CI associated with the Wilcoxon-Mann-Whitney test to a predefined noninferiority margin (in this case 2 mg). Covariate adjusted linear models will again be applied in the event that key characteristics are significantly different between the groups.

Sample size justification. Power for the Wilcoxon-Mann-Whitney derived noninferiority testing is based on 10,000 simulated trials. We simulated pain scores from a discrete distribution with median (interquartile range) 3 (2-5) [Kairaluoma, 2004]. Between the quartiles, the probability of each score was assumed constant. The distribution for each group was assumed to be the same. The sample size of n=50 per group provides 82% power to detect noninferiority in pain with a margin of 1.25. Similarly, opioid consumption was assumed to follow a truncated normal distribution with mean 2.5 mg and standard deviation 2 mg, and minimum value 0 mg. The sample size of n = 50 per group provides at least 95% power to detect noninferiority with margin 2 mg. Therefore, we will enroll 50 subjects for each of two treatments with a total enrollment of 100 subjects. To allow for dropouts, we will request a maximum enrollment of 120 subjects. Noninferiority in pain is tested first, and if significant, noninferiority in opioid consumption is tested. Under this hierarchical testing framework, no adjustment in alpha is necessary to control Type 1 error [Mascha, et al 2012].

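### Randomisation is stratified by unilateral versus bilateral surgery, but neither co-primary analysis uses the stratum, which costs precision if laterality predicts outcome

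*Combined protocol and SAP*

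**What the plan says.** Section 9 (Research Design and Methods) allocates subjects to "one of two treatment groups: (blocks of 4, stratified for unilateral vs. bilateral surgery". Laterality is the only stratification factor.

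Under Primary aim, the pain comparison is described thus: "The 95% confidence interval (CI) associated with the Wilcoxon-Mann-Whitney test will be derived for the group difference". Non-inferiority is concluded if the lower limit exceeds -1.25. Opioid consumption is handled in the same way, by "comparing the limits of a 95% CI associated with the Wilcoxon-Mann-Whitney test to a predefined noninferiority margin (in this case 2 mg". Neither description mentions a stratum.

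Covariates have one route into the analysis. Under Statistical methods: "Key characteristics that are significantly different (p<0.05) will be included as covariates in the analysis models". Primary aim repeats the rule for the fallback analysis: "these characteristics will be included as covariates in a linear model". Laterality is not named as an analysis stratum or covariate anywhere, and the power simulation has no laterality term.

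**The concern.** Balancing a factor by design removes its chance imbalance from the arm difference. An analysis that ignores the factor still counts the variation between strata as noise. If laterality predicts the outcome, the interval is therefore too wide and the true one-sided error at the margin falls below 2.5%.

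The covariate rule does not repair this. It selects factors that happen to be imbalanced, and stratified blocks keep laterality balanced. If another characteristic triggers the linear model, laterality still stays out.

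Pain is where this could matter. It is tested first, both outcomes must succeed, and its planned power is 82%, so it gates the overall claim. An effect of laterality is plausible but not documented: bilateral cases have two operated sides, and the anaesthetic volume per side also differs by laterality in Section 9.

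**Working it through.** **1. Inputs from the plan (Section 9).** 50 per arm; lower limit of a two-sided 95% interval (one-sided 0.025); margins 1.25 points and 2 mg; pain discrete with median 3 and interquartile range 2-5, flat between quartiles, same in both arms; opioid use normal(2.5, 2) truncated at 0.

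**2. Inputs that are assumptions.** Section 8 reports no pilot data, and no section gives the bilateral share *b* or the bilateral-minus-unilateral gap *d*. Ranges used: *b* = 20-50%, *d* = 0-2 pain points.

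**3. Reproducing the plan's figure.** The plan states: "The sample size of n=50 per group provides 82% power to detect noninferiority in pain with a margin of 1.25". With 25% of subjects spread over scores 0-2, 25% on 3, 25% over 4-5 and 25% over 6-10, the mean is 4.125, the variance 24.292 - 17.016 = 7.276 and the SD 2.70. Ten thousand simulated trials give 81.4% power.

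**4. Can the p<0.05 rule select laterality?** Blocks of 4 hold the difference in bilateral counts between arms to about 2. With 50 per arm, the smallest two-sided Fisher p for a difference of 2 occurs at 0 versus 2: 2 × (50×49)/(100×99) = 0.495. A difference of 4 gives at best 0.117; a difference of 6 (best p 0.027) is needed.

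Two provisions loosen the balance: "Misplaced blocks will be replaced successfully, or the patient excluded from further study participation" and "To allow for dropouts, we will request a maximum enrollment of 120 subjects". With 120 randomised and 20 lost at random, the lowest p was 0.11, and none of 16,000 trials (4,000 at each of 20, 30, 40 and 50% bilateral) reached p<0.05. Only losses that differ strongly by arm and laterality would change this.

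**5. Expected size.** The share of variance explained is R² = b(1-b)d²/SD², and the stratified-to-unstratified width ratio is √(1-R²).
- *b* = 0.5, *d* = 1: R² = 0.25/7.276 = 0.034, ratio 0.983.
- *b* = 0.5, *d* = 2: R² = 1.00/7.276 = 0.137, ratio 0.929. The unstratified one-sided error is then about 1-Φ(1.96/0.929) = 1-Φ(2.11) = 1.7%.

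Simulated rank intervals agree. Over *b* = 20-50%, the unstratified interval is about 1-2% too wide at a 1-point gap and 5-9% at 2 points (for example 2.00 against 1.84 at *b* = 0.5, *d* = 2).

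**6. Pain power.** Wilcoxon versus van Elteren, blocks of 4 within stratum, overall pain distribution held at the plan's, 10,000 trials per cell:

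| Bilateral | Gap | Unstratified | Stratified | Change (points) |
|---|---|---|---|---|
| 40% | 0 | 81.4% | 80.9% | -0.5 |
| 40% | 0.5 | 81.1% | 81.0% | -0.1 |
| 40% | 1 | 81.1% | 82.1% | +1.0 |
| 40% | 1.5 | 81.5% | 83.7% | +2.2 |
| 40% | 2 | 82.3% | 85.6% | +3.3 |
| 20% | 2 | 81.4% | 84.2% | +2.8 |
| 50% | 2 | 83.0% | 86.9% | +3.9 |

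Separately coded runs at 40% bilateral (5,000 trials per cell) gave 81.3% versus 82.2% at 1 point and 83.0% versus 86.1% at 2 points.

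**7. One-sided error with a true difference of 1.25** (30% and 50% bilateral). Unstratified: 2.6% at no gap, 2.2-2.4% at 1 point, 1.8% at 2 points. Stratified: 2.2-2.6% throughout.

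**8. Opioid use.** Power is at least 99.9% either way. Mean interval width at 40% bilateral, unstratified versus stratified: 1.36 versus 1.37 mg if use is equal, 1.37 versus 1.27 mg if mean bilateral use is 1.5 times unilateral, and 1.36 versus 1.07 mg if it is double.

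**The case against.** The strongest counter-argument is that the benefit may be nil. At a 0.5-point gap laterality does predict pain, yet stratifying changes power by -0.3 to 0 points; a gain appears only from about 1 point. The larger gains need a 2-point gap, which exceeds the non-inferiority margin itself, or a doubling of opioid use, and nothing in the documents supports either. The existing error is conservative, which is the safe direction for a non-inferiority claim. The change also takes more than naming a test: a stratified interval needs its weighting stated, and the plan's power was simulated for the unstratified version. Finally, other readings of the quartile rule give 73-87% baseline power, and the gains were not examined under those.

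All of this stands as a limit on importance. It does not remove the point. The plan leaves out of the analysis the one factor it chose to balance, its covariate rule cannot bring that factor back, and the possible loss from including it (at most about 0.5 points of pain power) is smaller than the possible gain.

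**Conclusion.** The concern holds as a missed gain in efficiency and calibration. The textual part is firm: no provision brings laterality into either co-primary analysis. The size is conditional. Over the assumed ranges, stratifying moves pain power by between -0.5 and +3.9 points. Opioid intervals become 5-7% narrower if mean bilateral use is 1.5 times unilateral, 17-22% narrower if it is double, and about 0.5% wider if use is equal.

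These figures rest on the assumed bilateral share and gap, and on the reading of the pain distribution that reproduces the stated 82%. The planned analysis remains valid: false non-inferiority is not inflated, and the 82% and 95% power statements, which refer to the unstratified test, are not undercut. The change is worth making because it is cheap, but the trial does not depend on it.

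**What to change.** Prespecify in Statistical methods that both co-primary comparisons are always stratified by unilateral versus bilateral surgery, whatever the baseline tests show:

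- If the rank method is kept, use a van Elteren test with the matching stratified Hodges-Lehmann 95% interval (the shifts that the test does not reject), and state the stratum weights.
- In any covariate-adjusted linear model, include laterality as a fixed term alongside whatever else is selected.

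The margins, sample size and testing order need not change. The stratum is known for every subject at randomisation, so no new data are required. The cost is a sentence or two of text and, preferably, a rerun of the power simulation for the stratified interval. If laterality has no effect on pain, the price is about 0.2-0.5 points of power.

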10. HUMAN SUBJECTS

Inclusion criteria for the trial will be: (1) undergoing unilateral or bilateral breast surgery with at least moderate postoperative pain anticipated; (2) analgesic plan includes a single-injection peripheral nerve block(s); and (3) age 18 years or older.

Exclusion criteria for the trial will be: (1) morbid obesity as defined by a body mass index > 40 (BMI=weight in kg / [height in meters]²); (2) renal insufficiency (preoperative creatinine > 1.5 mg/dL); (3) chronic opioid use (daily use within the 2 weeks prior to surgery and duration of use > 4 weeks); (4) history of opioid abuse; (5) any comorbidity which results in moderate or severe functional

limitation; (6) inability to communicate with the investigators or hospital staff; (7) pregnancy; (8) planned regional analgesic with perineural catheter placement; and (9) incarceration. We will recruit a maximum of 120 subjects. Selection for inclusion will not be based on race or socioeconomic status. The study population of interest includes men and women of all races and socioeconomic status. There will be no participants from vulnerable populations, such as pregnant women, children, or prisoners.

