11. RECRUITMENT AND PROCEDURES PREPARATORY TO RESEARCH

Study inclusion will be proposed to eligible patients prior to surgery by the investigators. Since the investigators will be contacting patients as part of their standard preoperative anesthesia consultation, HIPAA regulations will be adhered to. For women of childbearing age with the possibility of pregnancy, a sample of urine is always collected for a pregnancy test prior to surgery—regardless of study participation. Pregnant patients will be excluded from study participation.

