12. INFORMED CONSENT

If a patient desires study participation, written, informed consent will be obtained. An investigator or research assistant/coordinator (including regional anesthesia fellows) specifically trained in both study details and appropriate consenting procedures will attain verbal and written informed subject consent. The method of documenting consent will be using written informed consent form (including a written HIPAA consent form and UCSD Experimental Subjects' Bill of Rights).

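### A single randomisation block size of 4, not stated to be withheld from staff, makes about one third of assignments predictable on average to anyone who tracks allocations

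*Combined protocol and SAP*

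**What the plan says.** All references are to the combined protocol and SAP.

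- **Allocation.** Section 9, Preoperative Procedures: "Subjects will then be randomized using a computer-generated list and opaque, sealed envelopes to". The restriction on the list, given in brackets, is "blocks of 4, stratified for unilateral vs. bilateral surgery". No second block size is mentioned, and no sentence says who may know the size.
- **Who learns the allocations.** Section 9: "All blocks will be placed by a regional anesthesia fellow or resident under the direct supervision and guidance of a regional anesthesia attending". An attending may also do this without a trainee.
- **Who takes consent.** Section 12: "An investigator or research assistant/coordinator (including regional anesthesia fellows) specifically trained in both study details". Fellows therefore appear in both roles.
- **Judgements before the envelope.** Section 10 admits patients "undergoing unilateral or bilateral breast surgery with at least moderate postoperative pain anticipated". Section 11 adds: "Study inclusion will be proposed to eligible patients prior to surgery by the investigators". Section 9 has both sites viewed by ultrasound after consent, and a patient can be turned away at that stage on one clinician's judgement: "If one or both of the locations is unacceptable for block placement in the".
- **Safeguards.** Section 9 declares equipoise between the two techniques. The ultrasound rule removes a patient if either site is unsuitable, whichever arm would have come next. Under Statistical methods and Primary aim, key baseline characteristics that differ at p<0.05 enter the analysis models as covariates.

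**The concern.** Opaque envelopes hide the next assignment from someone who has only the envelope in hand. They do not hide it from someone who can count. Within a randomisation block of 4 at 1:1, once two patients have gone to one arm, the rest of that block is fixed. The stratum (unilateral or bilateral) is known before randomisation, so the count can be kept separately in each.

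This matters because eligibility is partly a matter of opinion. If the next assignment is known or well guessed, three decisions could come to depend on the arm: whether to approach a patient, whether enough pain is anticipated, and whether a site is acceptable. Anticipated pain bears directly on what the two primary hypotheses measure, namely recovery-room pain scores and operating- and recovery-room opioid use. Selection on it could make the arms differ in expected outcome, in either direction, before any treatment effect.

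**Working it through.** The plan states no predictability figure, so there is none to reproduce.

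**Inputs.** Block size 4 and two strata (section 9, Preoperative Procedures). Allocation 1:1, inferred from 50 subjects per treatment (section 9, Sample size justification), so each block holds two of each arm.

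**Step 1: certain assignments, all earlier allocations in the stratum known.** A 2+2 block has 6 equally likely sequences, hence 6 × 4 = 24 positions.

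- In the 2 sequences that begin with two of the same arm, positions 3 and 4 are both forced: 2 × 2 = 4.
- In the other 4 sequences only position 4 is forced: 4 × 1 = 4.
- Total 8/24 = 33.3%. A single block has either 25% forced (4 of 6 sequences) or 50% (2 of 6).

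Simulating whole lists with incomplete last blocks, and an assumed bilateral share of 30% or 50%, gives about 32.5 certain assignments per 100 subjects (95% range 28 to 37), or about 39 per 120 (34 to 45).

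**Step 2: best guess.** Always naming the arm with more places left in the block is right with probability 1/2, 2/3, 2/3 and 1 at positions 1 to 4. The mean is (1/2 + 2/3 + 2/3 + 1)/4 = 17/24 = 70.8%, against 50% by chance.

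**Step 3: incomplete tracking.** Nerve block placement is spread over fellows, residents and attendings, so one person may miss some allocations. Assume each earlier allocation is seen independently with probability p and the position in the block is known.

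- Position 3 is certain if the first two assignments match (1/3) and both were seen: p²/3.
- Position 4 is certain if both members of the arm already used up were seen: p².
- Average over four positions: (p²/3 + p²)/4 = p²/3.
- p = 0.75 gives 0.5625/3 = 18.8%. p = 0.50 gives 0.25/3 = 8.3%.
- Enumerating the same cases for the best guess gives 64.6% and 59.9%.

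**Step 4: varying block sizes.** Sizes were taken as equally likely. The guesser was assumed to know the set of possible sizes but not the size in use. Results come from simulated lists with strata of 25 to 100 subjects (full tracking) or of 25 and 75 (partial tracking).

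| Scheme | Certain, full tracking | Best guess, full tracking | Certain, 75% / 50% seen |
|---|---|---|---|
| Fixed 4 | 33.3% | 70.8% | 18.8% / 8.3% |
| 4/6 | 5.5-5.7% | 68-69% | about 1.5% / 0.2-0.4% |
| 4/6/8 | 2.2-2.4% | 67-68% | at most 0.5% / at most 0.1% |

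With partial tracking, the best guess under 4/6 is about 62.6% / 58.5%.

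A larger fixed size does less: by the same enumeration, fixed 6 leaves 25% certain and fixed 8 leaves 20%.

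**Step 5: cost in balance.** The largest imbalance at the end of a stratum is half the largest block: 4/2 = 2 now, 6/2 = 3 for 4/6, and 8/2 = 4 for 4/6/8.

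**The case against.** Permuted blocks of 4 with opaque, sealed envelopes form a complete and coherent scheme, and no section contradicts another. The protocol declares equipoise, which weakens any motive to steer. The ultrasound rule is symmetric: a patient is dropped if either site is unsuitable. Measured baseline differences reaching p<0.05 are adjusted for. Full tracking is a demanding assumption when several people place blocks. The remedy also barely lowers the best guess, and someone inclined to steer can act on a good guess as well as on certainty.

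Most of this stands, and it limits the weight of the point. None of it removes predictability. A symmetric rule applied by opinion can still be applied more or less strictly when the next arm is known. Adjustment reaches only recorded characteristics that cross the p<0.05 threshold. The examples in section 9 are age, sex, height and weight, and anticipated pain is not among them. The modest gain in best-guess accuracy is a real limit of the remedy. Its benefit is that it removes most of the certain predictions.

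A reader might infer that enrolment will in fact be steered. The documents do not support that: they show overlapping roles and an opportunity, not that anyone knows the size, keeps a count or acts on it.

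**Conclusion.** The point holds as an inexpensive improvement to the design, not as an error that undermines the trial. With one fixed block size of 4, a person who knows the size and tracks every earlier allocation in a stratum could be certain of about one third of assignments on average. One third is an average, not a ceiling, since a single block can reach 50%. It falls to 18.8% or 8.3% if 75% or 50% of earlier allocations are seen; those viewing rates are assumptions. No bias in pain or opioid use can be computed from the documents, and its direction is unknown.

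A reader might also infer a masking fault in the operating room, because section 9 says "Intravenous fentanyl will be administered for cardiovascular responsiveness to noxious stimuli at the discretion of the anesthesia provider" and operating-room opioid counts in Hypothesis 2. The documents do not say whether that provider knows the nerve block given. The plan promises masking of subjects and recovery-room nurses only, so no commitment is broken. That silence supports no finding, and none is made here.

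**What to change.** Generate the allocation list with randomly varying block sizes, for example 4/6 or 4/6/8, within the same unilateral and bilateral strata. Replace the stated size in section 9 with a sentence saying that block sizes vary at random and are withheld from staff who enrol, take consent or place nerve blocks.

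The cost is a regenerated list and one sentence, with no extra subjects, staff or procedures. The downside is the larger possible imbalance at the end of each stratum: at most 3 subjects (4/6) or 4 (4/6/8), instead of 2. Of the two, 4/6 gives up less balance and 4/6/8 leaves fewer certain predictions. Either is adequate.
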